### 3 Study Objectives

#### 3.1 Primary Objective

To determine whether SVR-12 rates are higher among those randomized to mDOT compared to those randomized to PN, among PWID treated for HCV at OTPs and community health centers.

#### 3.2 Secondary Objective 1

To examine the following outcomes overall and by randomization arm (mDOT compared to PN) among PWID treated at OTPs and community health centers:

- (i) Treatment initiation: whether a higher proportion of participants in the PN arm initiate treatment compared to mDOT arm;
- (ii) Adherence ( $\geq 80\%$  of prescribed medication taken): whether a higher proportion of those in the mDOT arm are adherent compared to PN arm;
- (iii) Treatment completion (finishing 100% of prescribed 12-week course): whether a higher proportion of participants in the mDOT arm complete treatment compared to PN arm;
- (iv) Drug resistance: whether the proportion who develop drug resistance is higher in the PN arm compared to mDOT arm;
- (v) Reinfection: whether (a) rate (incidence), and the (b) proportion who become reinfected with HCV is higher in the PN arm compared to mDOT arm;

Comparisons will be performed to determine the proportion of subjects in each arm who: a) initiate treatment; b) adhere to antiviral treatment; c) complete antiviral treatment; d) attain SVR (cure); e) develop drug resistance; f) reinfection. We will also conduct time to event analyses to examine drug resistance and reinfection outcomes. Subgroup analyses will be performed to assess differences in outcomes among those randomized to PN vs. mDOT in specific sub-populations.

#### 3.3 Secondary Objective 2

To examine factors associated with key study outcomes (treatment initiation, adherence, SVR, drug resistance and HCV reinfection) using quantitative and qualitative methods.

Quantitative methods: We will examine associations between psychosocial factors such as homelessness, co-morbid mental illness, poor social support, and high

levels of shame and stigma, with key study outcomes described above. It is hypothesized that these psychosocial variables are associated with lower rates of adherence and SVR in the PN arm, but not the mDOT arm; and associated with lower rates of treatment initiation in the mDOT arm, but not the PN arm.

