## 11.4 Sample Size Determination

Sample size N=300 per arm, or a total of N=600, was determined based on feasibility of recruitment from all sites during the study period. Power analysis for each hypothesis below is conservatively conducted based on a reduced sample size (N= 270 per arm, or N=540 in total) after considering 10% attrition rates. The target power is 80% with a two-sided significance level of 0.05. To this end, minimally detectable effect sizes and widths of 95% confidence intervals were computed with those parameters and the sample size after attrition.

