### Statistical Model

The precision of proportion of participants who develop resistance or reinfection will be determined with 95% confidence intervals (CIs) calculated using exact binomial methods. To identify factors associated with resistance or reinfection, we will conduct bivariate analysis using (exact) logistic regressions for both continuous and dummy-coded categorical variables. A series of bivariate analyses will be followed by a multivariable logistic regression that includes all factors significant in the bivariate analysis at a two-sided 0.05 significance level. All analyses will be separately conducted for each of resistance and reinfection outcomes. For the examination of association between resistance and adherence in particular, a multivariable logistic regression will also be applied in which overall adherence will be the primary predictor in the presence of other factors identified in the bivariate logistic regression analysis. In all multivariable analysis, the mDOT arm indicator will be included for adjusting purpose.

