### Power analysis

With a total of N=540 after attrition, the expected 95% confidence intervals are (7.7%, 12.8%) and (3.5% and 7.2%) for the resistance and reinfection rates, respectively. For the bivariate analysis, any binary variable with odds-ratio (OR)  $\geq 1.8$  (or 7% vs. 14.4%) for resistance and OR  $> 3.3$  (or 2.5% vs. 7.8%) for reinfection will be identified with >80% power; and any continuous variable with OR $>1.6$  and OR $>2.1$  per 1 SD unit changes will be detected for resistance and reinfection, respectively. In the multivariable analysis, binary variables with OR  $> 2.5$  (7% vs. 16.2%) and OR  $> 4.0$  (2.5% vs. 9.3%) and continuous variables with OR 1.8 and OR $>2.5$  per 1 SD unit change will be detected for resistance and reinfection, respectively, with >80% power, expecting that as large as 30% of variation of each variable will be explained by the other variables in the models for aim 2 analyses. Likewise, for detecting association between a continuous

adherence rate and resistance, OR  $\geq 1.8$  per 1 SD unit change will be detected with  $> 80\%$  power.

## 11.12 Analytic plan for Aim 3

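### Protocol 11.11 picks resistance and reinfection factors by an unlisted p<0.05 screen and refits them on the same data; the search should be pre-specified, penalised and labelled exploratory

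*Protocol*

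**What the plan says.** Protocol 3.3 (Secondary Objective 2) sets the aim: "To examine factors associated with key study outcomes (treatment initiation, adherence, SVR, drug resistance and HCV reinfection) using quantitative and qualitative methods". Its quantitative paragraph gives examples of psychosocial factors (homelessness, mental illness, social support, shame and stigma) as an open list.

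Protocol 11.11, Statistical Model, gives the method for two of those outcomes:

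- Candidates are tested singly: "we will conduct bivariate analysis using (exact) logistic regressions for both continuous and dummy-coded categorical variables".
- Those that pass go forward: "A series of bivariate analyses will be followed by a multivariable logistic regression that includes all factors significant in the bivariate analysis", the screening level being two-sided 0.05.
- The procedure is run twice: "All analyses will be separately conducted for each of resistance and reinfection outcomes".
- Arm is forced in: "In all multivariable analysis, the mDOT arm indicator will be included for adjusting purpose".
- For the link between resistance and adherence, adherence is the named predictor, and its covariates are those that passed the bivariate step.

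The Power analysis paragraph of 11.11 gives detectable odds ratios for both the bivariate and the multivariable step. It says that factors beyond the stated size "for reinfection will be identified with >80% power".

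The SAP has no section on resistance or reinfection, so 11.11 governs. The SAP's general rule, at the end of its section 3.3, is a two-tailed 0.05 for every test.

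**The concern.** A factor reaches the final model because it was significant in these data, and it is then judged again in these data. The final p-values and confidence intervals take no account of that selection. With an open candidate list, a reader cannot tell how many factors were tried before some were reported. Two things follow. A report of associated factors may contain at least one that is pure chance, and the odds ratios that survive tend to be too far from 1. The second effect is worse when events are few, as they are here. The covariates of the adherence-resistance model are chosen by the same gate, so confounders would be kept or dropped by p-value.

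The investigators already apply the relevant safeguards elsewhere. SAP 5.4 uses p<0.01 to declare baseline imbalance and cites multiplicity as the reason, and SAP 7 heads the mediation analysis as exploratory. Neither safeguard appears in Protocol 11.11.

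**Working it through.** **Inputs.** From Protocol 11.11: N = 540 after attrition; resistance 10% (0.10 × 540 = 54 events); reinfection 5% (0.05 × 540 = 27 events); screen at two-sided 0.05; arm forced into the final model. The level of the re-test is not stated in 11.11. I take 0.05 from Protocol 11.4 ("The target power is 80% with a two-sided significance level of 0.05") and from the SAP's general rule. The number of candidates k is not given, so 5, 9 and 20 are assumptions. Nine is the number of characteristics listed for subgroup analysis in Protocol 11.10.

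**1. The plan's own power figures.** With p̄ = (p1 + p2)/2 and n per group,

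power = Φ{ [|p2 − p1| − z√(2p̄(1 − p̄)/n)] / √[(p1(1 − p1) + p2(1 − p2))/n] }.

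- Resistance, 7% vs 14.4%, n = 270, z = 1.96: (0.074 − 1.96 × 0.0266)/0.0264 = 0.83, so power is 79.6%.
- Reinfection, 2.5% vs 7.8%: 79.7%.
- Multivariable step, n = 270 × (1 − 0.30) = 189: 80.0% (7% vs 16.2%) and 80.4% (2.5% vs 9.3%).

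The stated power of about 80% is reproduced for the percentages. As a side point, 7% vs 14.4% is an odds ratio of (0.144/0.856)/(0.07/0.93) = 2.23, not the printed 1.8. An odds ratio of 1.8 from 7% gives 11.9%, for which power is about 50%.

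**2. At least one false factor, all candidates null.** For independent tests the screen gives 1 − 0.95^k. The final-model column comes from simulating the whole procedure (N = 540, 54 or 27 events, screen, refit with arm, re-test at 0.05).

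| k | Screen, 1 − 0.95^k | Final model, per outcome |
|---|---|---|
| 5 | 22.6% | about 19-20% |
| 9 | 37.0% | about 28-37% |
| 20 | 64.2% | about 37-61% |

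The lower ends are for factors correlated at about 0.33. That value corresponds to the plan's own allowance that up to 30% of each variable's variation is explained by the others. For k equally correlated factors, R² = (k − 1)ρ²/(1 + (k − 2)ρ); with k = 20 and ρ = 0.33 this is 19 × 0.1089/6.94 = 0.298.

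A separate set of runs (2,000 per setting, binary or continuous factors, Wald or Fisher-exact screen) gave 16-23%, 28-34% and 53-63% for independent factors. At correlation 0.3 it gave 17-19% for k = 5 and 35-49% for k = 20. The result therefore does not depend on using Wald tests.

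**3. What the refit removes.** With independent factors, almost nothing: for k = 20 binary factors and resistance, 63.0% after the screen and 61.5% after the refit. With correlation 0.5 and k = 20 it removes a good deal: from about 47% to 27-29%.

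**4. Inflation of retained odds ratios.** For a binary factor at 30% prevalence (assumed) with a true odds ratio of 1.8, the average estimate among analyses that pass the screen is about 2.2 with 54 events and about 2.8 with 27 events.

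**5. Price of a multiplicity adjustment.** The formula in step 1 at the first Holm level takes the plan's bivariate effects from about 80% power to about 61% at 0.05/4 and about 58% at 0.05/5.

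**The case against.** The strongest reply is that this is a secondary search for associations. SVR is the sole primary outcome, Protocol 3.3 speaks of examining factors, and the power paragraph is an ordinary detectable-effect statement. That is fair. A reader might infer that the plan presents each factor as a confirmatory finding, but the documents do not go that far. What remains is narrower: a claim to identify factors, with nothing to tell the reader that a search took place.

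A reader might also take the larger percentages as the error rate of a given factor, or as a typical figure. Neither is supported. They are family-wise rates per outcome with every candidate null. The top of the range needs both 20 candidates and no correlation, and the documents fix neither. Nor is the refit worthless in general; step 3 shows that correlation makes it useful.

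Two objections to possible remedies also stand. Strict adjustment is not a slight cost: about 20 points of power is a great deal with 27 to 54 events. And a list confined to the psychosocial factors of Protocol 3.3 would omit injecting, although Protocol 2.1 reports reinfection rates by ongoing injecting (5.2 vs 3.2 per 100 person-years) and Protocol 8.6 schedules an injection-behaviour assessment at every post-treatment visit. Moreover, the directional hypothesis in 3.3 covers adherence, SVR and initiation, not resistance or reinfection, so using those factors here is a choice to be declared.

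It might finally be inferred that such findings would decide who is offered treatment. The documents describe no such use.

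**Conclusion.** The concern holds as a defect of a secondary analysis. Protocol 11.11 states a definite rule, screening at 0.05 and refitting on the same data, without a candidate list, adjustment or exploratory label, and no SAP section replaces it. At the plan's own N and event rates, with all candidates null, the chance of at least one false factor per outcome is roughly one in five with 5 candidates and between about 37% and 61% with 20. Real associations that pass are exaggerated.

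This rests on an assumed number of candidates, on a 0.05 re-test level inferred from Protocol 11.4 and the SAP, and, for the inflation figures, on a 30% prevalence and a true odds ratio of 1.8. The primary SVR test is unaffected. This is a cheap improvement to make, not a threat to the trial's main conclusion.

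**What to change.** In Protocol 11.11, or in a new SAP section on these outcomes:

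1. Remove the bivariate p<0.05 gate.
2. For each outcome, fit one pre-specified multivariable logistic model with the arm indicator and a short list fixed before analysis: the psychosocial factors of Protocol 3.3 (housing, mental illness, social support, shame/stigma), plus post-treatment injecting behaviour for reinfection and overall adherence for resistance. State how repeated injecting reports are summarised.
3. Use Firth-penalised likelihood. Counting shame/stigma as one term, the model has 1 + 4 + 1 = 6 coefficients, so about 54/6 = 9 events per coefficient for resistance and 27/6 = 4.5 for reinfection.
4. Label the factor search exploratory. Report odds ratios with 95% confidence intervals and the number of factors examined, and do not describe factors as identified.
5. Treat Holm adjustment as optional, given the fall in power to about 58-61% with 4-5 factors. In the simulation, a fixed list tested at 0.05/k held the chance of any false factor to 2.6-4.8%. The investigators should make that trade knowingly.

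The cost is a paragraph of wording and a small code change, using data already scheduled for collection. The downside is that factors outside the list can be reported only as hypothesis-generating.

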## 4 Study Design

### Overview of study approach

This is a multi-site national study (8 U.S. cities), where up to 1000 HCV-infected PWIDs (injecting illicit substances within 3 months of screening) will be randomized to either PN plus weekly or biweekly blister pack dispensation versus mDOT. Among patients who go on to initiate HCV treatment (n=600 targeted) with a once-daily combination regimen of fixed-dose sofosbuvir/velpatasvir, a comparison will be conducted of the proportion of patients in each arm who: (a) optimally adhere ( $\geq 80\%$ ), (b) complete treatment, (c) achieve SVR, and (d) develop resistance. The primary outcome will be SVR. The 8 sites offer geographic and policy diversity: New York City, Baltimore, Providence, Boston, Morgantown, Seattle, San Francisco, and Albuquerque.

Participants will be recruited from diverse venues: OTPs, community health centers, syringe exchange programs, community-based organizations, homeless programs, and cohorts established by research studies. The clinical sites will determine eligibility based on clinical records, or on-site testing including HCV tests (anti-HCV and HCV viremia). Study participants will be screened, consented and enrolled on-site at OTP and non-OTP settings. There will be differences in linkage, engagement and outreach at each site. These procedures will be documented in site specific operating manuals.

Patients will be randomized to one of two models of care: patient navigation (PN) vs. modified directly observed treatment (mDOT). Patients enrolled from OTPs who are receiving methadone and randomized to mDOT will receive doses of once daily medication at the same time as they receive methadone. Patients enrolled from community health settings and randomized to mDOT may receive observed doses through use of miDOT (emocha Mobile Health, Inc.), a mobile health app on a smartphone, or at the CHC. Subjects randomized to PN will receive a standardized PN intervention. Sites also have the option to offer all subjects optional additional support through a peer-led support group.

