## 5.4 Randomization

Up to 1000 patients will be recruited, with patients randomized to PN or mDOT in a 1:1 ratio (500 subjects in each group) in variable block sizes of 2-6 via central, computer-generated randomization provided by the UNM Statistical and Data Coordinating Center (SDCC). Randomization will occur in blocks to ensure comparison groups of approximately equal size. Given that the intervention will not be blinded, block size will vary to prevent anticipation of treatment arm assignment.

Two special randomization strategies (stratification and blocking) will be used to avert imbalances in prognostic factors or treatment settings, and to ensure comparison groups of approximately equal size. Participants will be stratified by 3 factors: city, OTP vs. community health center and stage of liver disease (cirrhosis v. no cirrhosis).

In addition, adaptive re-weighting of random allocation in a pseudo urn randomization fashion will be made when N~300 has been enrolled to balance the sample size between mDOT and PN arms. Specifically, as we hypothesize that number of randomized subjects who will initiate treatment will be larger in the PN arm, unbalancing between arms is likely to occur during the course of the study. Of note, therefore, a randomized subject will not necessarily be a clinical treatment subject but will be included in the comparison of treatment initiation.

To adjust for this potential unbalance, we will adjust randomization based on observed allocation ratio at the middle of trial if the overall allocation difference is greater than 5% (i.e., <47.5% vs. 52.5%).

Storage and dispensing of random allocation codes will be made in a centralized fashion. The UNM SDCC will generate and store the codes for all sites and types of clinics, and will be embedded into the Research and Electronic Data Capture (REDCap) data management system in the backend so that the identification of a treatment assignment will be ready and immediate without contacting the coordinating center when requested through the REDCap electronic request form by a responsible research staff at the sites whenever a new eligible participant is enrolled. The UNM SDCC will also be responsible for conducting re-weighted randomization, if necessary, at the middle of the trial.

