### Statistical Model

Multivariable logistic regressions will be applied to test the overall effectiveness of mDOT or PN on the five binary outcomes (success vs. failure) with the SVR rate as the primary outcome. The arm indicator will be the predictor for each outcome. With respect to adherence outcome in particular, repeatedly measured adherence will be analyzed (using 6 post-baseline time points and adherence as a continuous measure) applying a mixed effects linear model to test if the two arms are significantly different. This model accounts for within-subject longitudinal outcome correlation by taking the subject-level intercept as random. All models will include potential confounding variables that are significantly different between the two arms; the sites will be included as a covariate as well. Likewise, mixed effects logistic regression will also be applied to test the significance of PN and DOT on repeatedly-measured undetectable HCV VL throughout the intervention period, adjusting for substance use in addition to other confounding variables. Changes in illicit drug use will be analyzed using urine toxicology data from each visit, counting the “person-month” as a unit of analysis, and analyzing the percentage of person-months that are positive for use of illicit drugs during the study period using a t-test or Mann-Whitney test.

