### 6.2.1 Main subgroup effects

The main effect of subgroup indicators (e.g., OAT vs. CHC) will be assessed via comparing outcome between levels of each subgroup in multivariable models adjusting for the care model arms and site, that is, the multivariable logistic regression model that include: a subgroup indicator, site and the arm indicator in the following form:

$$\text{Logit}(P(\text{SVR})) = b_0 + b_1 * \text{Subgroup Indicator} + b_2 * \text{TRT} + b_3 * \text{Site1} + \dots + b_9 * \text{Site7}.$$

The analysis results will be graphically displayed in a forest plot.

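### The resistance and reinfection factor models in protocol 11.11 force in only the arm, not site, so a between-city difference can be credited to a patient factor that merely tracks the city

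*Protocol*

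**What the plan says.** Section 11.11 (Statistical Model) has two steps. In the first, "we will conduct bivariate analysis using (exact) logistic regressions for both continuous and dummy-coded categorical variables". The second reads: "A series of bivariate analyses will be followed by a multivariable logistic regression that includes all factors significant in the bivariate analysis", with entry at two-sided 0.05. One term is forced in: "In all multivariable analysis, the mDOT arm indicator will be included for adjusting purpose". Neither step names site, city, a random effect or a clustered variance. The candidate factors are not listed.

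Elsewhere the plan does adjust for site. In the 11.10 models, "the sites will be included as a covariate as well". The closest parallel is SAP 6.2.1, which asks which patient factors relate to SVR and uses "multivariable models adjusting for the care model arms and site". City is also a randomisation stratum (5.4): "Participants will be stratified by 3 factors: city, OTP vs. community health center and stage of liver disease". The SAP covers SVR, initiation, completion and adherence, but not resistance or reinfection, so 11.11 is the only text on these two outcomes.

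**The concern.** Secondary Objective 2 (3.3) asks which factors go with resistance and reinfection, among other outcomes. Randomisation stratified by city balances city between the arms. It does nothing for patient factors, which are observed rather than assigned. Table 2 shows how strongly some of them depend on city: HIV runs from 2% to 70%, Latino ethnicity from 0% to 65%, and African-American race from 2% to 75%.

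If resistance or reinfection differs between cities for any reason (local transmission, harm-reduction coverage, clinic practice), a pooled single-factor model gives that difference to whichever factor is common in the high-rate cities. The bivariate p-value then decides entry to the multivariable model, which has no site term to remove the effect. The answer to who becomes reinfected or resistant could then be a proxy for where they were treated.

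**Working it through.** **1. The plan's own figures.** Section 11.11 (Power analysis) uses N=540, two-sided 0.05 and power above 80%. For two equal levels of n each, power = Φ{[d√n − 1.96√(2p̄(1−p̄))] / √(p₁(1−p₁)+p₂(1−p₂))}.

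- Bivariate, n=270, 7% vs 14.4%: d√n = 0.074×16.43 = 1.216; 1.96×0.4371 = 0.857; denominator 0.434; Φ(0.828) = 79.6%. For 2.5% vs 7.8%: 79.7%.
- Multivariable, n = 270×(1−0.30) = 189: 7% vs 16.2% gives 80.0%; 2.5% vs 9.3% gives 80.4%.

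The stated power reproduces for these pairs of rates.

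**2. How much of each factor is explained by city.** With equal-sized cities, R² = variance of the eight Table 2 percentages / [p̄(1−p̄)].

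- HIV: 0.0541/(0.275×0.725) = 27%
- Latino: 0.0514/(0.210×0.790) = 31%
- African-American: 23%
- Unstable housing and psychiatric illness: 12% each
- Cirrhosis: 11%
- Sex: 6%

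**3. False-positive rate without a site term.** Simulation of 540 people in eight near-equal cities (67 or 68 each, an assumption). Factor prevalence is taken from Table 2, overall outcome rates are 10% (resistance, 54 events) and 5% (reinfection, 27 events), and the factor has no effect within a city. City rates were drawn from a beta distribution with variance ICC×p(1−p). The ICC is an assumption because the documents give none. There were 40,000 replicates, comparing a pooled score test with a city-stratified one. Ranges cover both outcomes.

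| ICC (proportion scale) | HIV, Latino, African-American | Housing, psychiatric illness | City-stratified test |
|---|---|---|---|
| 0 | 5% | 5% | 5% |
| 0.01-0.02 | about 7-10% | about 6-7% | about 5% |
| 0.05 | about 12-16% | about 9% | about 5% |

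An ICC of 0.05 is a large spread. The 10th-90th percentile of city rates is about 3-19% for resistance and 0.5-11.6% for reinfection.

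**4. The same check on the logit scale.** City intercepts are normal with SD s.

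- Resistance, s=0.5 (city rates 5-16%): HIV 9.9%, Latino 10.2%, African-American 9.1%; other factors 6.1-6.9%.
- Resistance, s=0.8 (3-20%): 16.1%, 17.1%, 14.3%; others 7.6-10.1%.
- Reinfection, s=0.5: 5.6-7.6% across all factors.
- Reinfection, s=0.8: HIV 11.0%, Latino 11.7%, African-American 10.2%; others 6.2-7.6%.

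On this scale the inflation is smaller for reinfection than for resistance. A factor unrelated to city stays at about 5% throughout. The city-stratified test gives 4.5-5.2% in every setting.

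**5. Power after adding site.** Replace n by 270×(1−R²).

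- Latino: 270×0.69 = 186, giving 64% at both bivariate targets.
- HIV: 270×0.729 = 197, giving 66%.
- Sex: 270×0.94 = 254, giving 77%.

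The bivariate targets therefore fall from about 80% to about 64-77%. If site is the only other term, power at the multivariable targets is about 79-90%.

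**The case against.** - **The site sentence in 11.10 may be meant to reach further.** That paragraph speaks of five binary outcomes and of all models, while its heading lists four outcomes. Its scope is therefore unclear. But resistance and reinfection would make six, the paragraph describes models with arm as the predictor, and 11.11 sets out its own procedure with its own forced term. A one-line statement that site carries over would settle the point.
- **City could be screened as a candidate factor.** Section 11.11 does not rule this out. If it were done, final-model error would be about 2.7-5.1%. The section does not require it, and the bivariate results would still be unadjusted.
- **A bivariate test concerns the crude association, and this is exploratory work.** This is fair: an association that runs through city is not false as description. It is misleading when it is read as a patient factor, which is the stated aim.
- **Table 2 holds planning figures and has flaws.** The Maryland African-American entry prints 75% beside a count of 65, and SAP 5.4 reports few participants with cirrhosis. The exact R² values are therefore approximate. The wide spread for HIV and Latino ethnicity does not hang on those entries.
- **The cost is not trivial.** This stands, both for the power loss and for fitting seven site terms to about 27 reinfections.

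**Conclusion.** As written, 11.11 omits a likely confounder that the plan adjusts for in 11.10 and in SAP 6.2.1. The direction of the error is clear. Its size depends on a between-city variance that the documents do not give: none if cities do not differ, modest at an ICC of 0.01-0.02, and reaching about 12-16% for the three most city-linked factors at 0.05.

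Four stronger readings are tempting and are not supported:

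- That the error rate is two to three times 5% as a fact. This needs both a strongly city-linked factor and substantial city variation. At ICC 0.05, housing and psychiatric illness stay below twofold.
- That the reinfection rates in section 2.1 (3.2 to 30 per 100 person-years) show city differences. They compare risk groups, not cities.
- That every SAP model includes site. The SVR imputation (5.3.1) and the mediation analysis (7) name no site term.
- That the arm comparison is distorted in the same way. Allocation was stratified by city.

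The point concerns secondary, factor-finding analyses. It is worth correcting because the remedy is cheap, and it does not threaten the primary result.

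**What to change.** State in 11.11, and in the SAP if these outcomes are added there, that every bivariate and multivariable factor model for resistance and reinfection is stratified on or adjusted for site, whatever the p-value for site. Use exact or conditional logistic regression with site as the stratum, since exact logistic regression is already named in 11.11, or a site random intercept. Either is preferable to seven fixed site terms, because 540×0.05 = 27 reinfections is only about 3 per city. Conditioning removes all between-city confounding; a random intercept estimated from eight cities removes it only in part.

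Restate the bivariate detectable odds ratios in the 11.11 power paragraph with an allowance for the share of each factor explained by site. While doing so, correct the printed pairing for resistance: 7% vs 14.4% is an odds ratio of (0.144/0.856)/(0.07/0.93) = 2.23, not 1.8. Note also that the 30% allowance in the multivariable statement is roughly used up by site alone for HIV (27%) and Latino ethnicity (31%), leaving little for other covariates.

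The cost is one sentence and a revised power paragraph, with no new data. The price in the analysis is the fall in bivariate power to about 64-77% at the stated targets, and cities without events contribute nothing to a conditional fit.
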